The present research group previously developed and evaluated a lifestyle change program focused on obesity prevention in Mexican schoolchildren in a face-to-face format, where positive results were obtained.²² Given the current situation due to COVID-19, this program was adapted to an online format to evaluate its effect through a pilot randomized controlled trial.

Explanation for the choice of comparators

The control group will be of children from the same public school as the children in the intervention group. The risk of contamination is reduced by not having face-to-face classes, but it is not completely eliminated, since there may be participants who take classes in the same group and interact online. Even so, the results will be valid if significant differences between groups are observed, as we observed in a previous study, because the previous situation would reduce the effect of the intervention.

OBJECTIVES

Primary objective

- To evaluate the effect of an online lifestyle intervention on the BMI Z-score of Mexican schoolchildren at 4 months during the COVID-19 pandemic in the intervention group compared to a control group.

Secondary objectives

- To evaluate the effect of an online lifestyle change intervention on waist circumference, body fat, physical activity and sedentary behaviors, food consumption, nutrition knowledge and quality of life of Mexican schoolchildren at 4 months during the COVID-19 pandemic in the intervention group compared to a control group.

- To evaluate the effect of an online lifestyle intervention on the retention, participation and acceptance of Mexican schoolchildren at 4 months during the COVID-19 pandemic in the intervention group.

MATERIAL AND METHODS

Study design

This is a pilot randomized controlled trial blinded to assessors, with 4-month follow-up. It is a pilot study, because we want to evaluate the effect and feasibility of the online intervention, to later carry out a definitive study considering an adequate sample size. The study will consist of two parallel arms, of superiority and with 1:1 allocation ratio.

To carry out this protocol, the SPIRIT 2013 guidewas followed.²³ The protocol was approved by the Research Ethics Committee of the Nursing Department of the University of Sonora (CEI-ENFERMERIA-EPM-003-2020) and registered on the Clinical.trials.gov platform (NCT04772859).

Participants

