Children from a public elementary school in Hermosillo, Sonora will be invited to participate in the study. It is worth mentioning that this public school is not representative of all the schools in Hermosillo, Sonora. Hermosillo is a city of about 884,273 inhabitants and around of 392 public elementary schools. It is located in the state of Sonora, in northwestern Mexico. Because the program is entirely online, students who agree to participate will take the intervention from home.

Sample size

No studies of online lifestyle interventions to prevent obesity in schoolchildren during the pandemic were found to obtain the effect size and standard deviation needed to estimate the study sample size. So, we decided that it would be a pilot study of at least 50 participants and no more than 70. This was decided considering our logistical capacity, which implies measuring the response variables at home in a period of 2 weeks, in addition to being able to provide intervention, among other things. The invitation will be made to all students from fourth to sixth grade of a public school in Hermosillo Sonora.

Eligibility criteria

Sign the consent and informed assent and complete the anthropometric measurements and lifestyle questionnaires.

Inclusion criteria

- 4th, 5th and 6th grade students from the participating elementary school.
- Have access to the internet.
- Have an electronic device (eg computer, laptop, tablet or smartphone).
- Nutritional status: normal weight, overweight or obesity.

Exclusion criteria

- Have a medical condition that affects body weight.
- Taking medication that affects body weight.
- Take another intervention that affects body weight.
- Have a condition that prevents physical activity.
- Withdraw informed consent or assent.
- Have a sibling participating in the study.

Implementers

The lifestyle intervention will be implemented by a Nutritionist and two interns from the Bachelor's Degree in Physical Culture and Sports from the study team. In

addition, there will be the support of interns from the Nutritional Sciences Bachelor of the University of Sonora.

Interventions of the study

Online lifestyle intervention

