The program will center on establishing health-related goals such as increasing consumption of fruits and vegetables, increasing physical activity time, decreasing hours spent in front of a screen, and reducing consumption of sweetened beverages. The program also will include the use of self-monitoring and positive reinforcement.

Physical activity sessions: Classes will be implemented 3 days a week for 30 minutes each. Children will work on developing different skills such as: flexibility, strength, elasticity and resistance. The Zoom digital platform will be used for the online (live) sessions. The classes will be recorded, in case the children want to do a class later.

Parent's participation: Parents who agree to participate in the program will be given a user to access a web page (www.salud-nutricional.com), where children's activities will be uploaded. This will be used to upload nutrition information, parenting activities, and study questionnaires. A private Facebook group will be created to upload teaching material (videos, infographics, messages and images) on a weekly basis. The difference between using the website and Facebook is that on the page the participants will be able to have the information ordered, upload their activities and study questionnaires. The topics addressed each week will be the same as those seen with the children in the nutrition sessions. On Facebook, they will have spaces for comments, questions, feedback and social support.

Control group: The control group will receive general nutrition recommendations at the beginning of the program, based on the Nutrition and Physical Activity Guidelines in the Context of Overweight and Obesity in Mexican Population.²⁴ A digital brochure will be sent in online format to the mail or through the WhatsApp application to parents. Upon completion of the study, they will be offered access to the materials from all the onlie lifestyle sessions, as well as physical activity videos for children recorded by the physical activity team.

Outcomes

The primary outcome is the change of the BMI Z-score from baseline to 4 months between the intervention group and the control group. The change in BMI Z-score for each individual will be obtained by subtracting the BMI Z-score value at 4 months minus the baseline value. The difference between groups will be obtained by subtracting the mean of the change in the intervention group minus that of the control.

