Secondary outcomes will include the differences in waist circumference, body fat and relative fat mass, physical activity and sedentary lifestyle, quality of life, participation, attendance and nutrition knowledge. The categorical variables such as: food consumption and acceptance, will be evaluated with differences in proportions.

Recruitment

To invite the participants, school directors will first be contacted to invite them, inform them about the objectives and activities of the intervention. Fourth, fifth and sixth grade students from a public elementary school in Hermosillo, Sonora, Mexico will be invited to participate. It will seek to have a space in the students' online school classes, where parents will be invited to attend. A small presentation will be made with the invitation, objectives and activities of the intervention. During the same meeting, they will be sent via chat the link to a web page where they can find the the consent and informed assent and a personal data questionnaire to evaluate inclusion and exclusion criteria. They must be read and signed by parents and children online. Children may participate, even if the parents decide not to get involved in their part of the intervention.

Randomization

The measurements of the study will be carried out in a period of 2 weeks. Once the measurements are completed, the participants who meet the inclusion/exclusion criteria will be randomized to one of two groups: the “online lifestyle intervention” group or the control group. An independent person of the recruitment and

intervention of the study will receive a database, only with the codes and the basic variables of the study (BMI Z-score, sex and age) to perform the allocation of the participants. This will be based on a random block sequence, stratified by BMI Z-score and sex, with an allocation ratio of 1:1. The random number sequence will be generated using the randomization software available on the website: <https://randomizer.org/>. Since the assignment will be made in a single moment and without the knowledge of the participants, its concealment will be guaranteed. Participants will be explicitly informed to the assigned group.

Outcome measures

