- **Personal information.** The first step for the screening of the participants consists of an online questionnaire of personal data. This will be sent at the time of the invitation to the program. Personal data of the child, internet access and electronic device, if they have a disease, if they take medications or perform extra interventions that may affect body weight will be asked. In addition, the email and education leve lof the parents will be asked.

Withdrawal of participants

Participants may withdraw from the study at any time they wish, being able to inform the reason or not.

Statistical Analysis

The normality of the data will be evaluated with the Shapiro Wilk test. Data will be presented as mean and standard deviation (mean \pm SD) or median and interquartile ranges according to their distribution. An independent samples t-test or Mann-Whitney U test will be used to analyze the difference in BMI Z-score and changes in secondary outcomes between groups. A chi-square test will be used to make comparisons on categorical variables. Two-tailed tests with $p \leq 0.05$ will be used as the criterion for statistical significance.

Data will be analyzed with an intention-to-treat analysis. If participants decide to withdraw from the intervention, they will be asked if the measurement at 4 months can be obtained to have at least the primary outcome for inclusion in the intention-to-treat analysis. If data is not obtained for any reason or subjects were excluded due to a protocol violation, they will be replaced by their baseline measurement.

Results will focus on change in the primary study variable (BMI Z-score), while changes in secondary variables and sub-analyses (sex and BMI: normal, overweight/obese) will be considered exploratory only. For data analysis, NCSS version 10 software (Number Cruncher Statistical System for Windows, Kaysville, UT, USA) will be used.

Confidentiality

Identifiable information and will be kept confidential. Each participant will be assigned a code, therefore, their identifiable information will appear with that code and not with names. Only the physical files will keep the names, which will be kept by the principal investigator of the study, in a safe place. Only the study team may have access to the database, for their purposes.

Declaration of interest

The authors did not report any potential conflicts of interest.

REFERENCES

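### Minor precision point: the primary comparison of change in BMI Z-score does not use the randomisation stratifiers; the test is valid but may leave some precision unused

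*Combined protocol and SAP*

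**What the plan says.** All references are to the combined protocol and SAP.

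- **Randomization:** "This will be based on a random block sequence, stratified by BMI Z-score and sex, with an allocation ratio of 1:1". Cut-points for BMI Z-score and block size are not given.
- **Outcomes:** "The change in BMI Z-score for each individual will be obtained by subtracting the BMI Z-score value at 4 months minus the baseline value". The treatment effect is the raw difference between the arms' mean changes.
- **Statistical Analysis:** "An independent samples t-test or Mann-Whitney U test will be used to analyze the difference in BMI Z-score". The same section says "The normality of the data will be evaluated with the Shapiro Wilk test", but gives no cut-off, does not say to which data the check applies, and does not say what triggers the Mann-Whitney test.
- **Statistical Analysis, last paragraph:** sex and BMI category return only as "sub-analyses (sex and BMI: normal, overweight/obese) will be considered exploratory only".
- **Sample size:** the total is 50 to 70, set by logistics. The authors found no study from which "to obtain the effect size and standard deviation needed to estimate the study sample size".
- **Study design:** the pilot is meant "to later carry out a definitive study considering an adequate sample size".

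No covariate-adjusted or stratified comparison of the arms appears anywhere.

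**The concern.** Stratified randomisation balances the arms on BMI Z-score and sex. If those factors predict change, an unadjusted test still counts their share of the variance as noise. Its standard error is then larger than the design requires: the interval is wider, power is lower, and the test rejects too rarely under the null.

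Subtracting baseline already removes most of the stable difference between children. What may go unused is only the remaining association of baseline BMI Z-score and sex with change. Recruitment is capped at 70, so precision cannot be bought with more children, and both covariates are already collected.

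**Working it through.** **Inputs from the documents.** Total n 50 to 70, 1:1 allocation, two-sided 0.05, outcome is change in BMI Z-score. There is no power, SD, effect size or correlation, so there is no planned figure to reproduce. Everything else below is assumed.

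**1. Scale.** Detectable difference at 80% power, normal approximation: (1.960 + 0.842) × √(2 / n per arm).
- 25 per arm: 0.79 SD of change
- 30 per arm: 0.72 SD
- 35 per arm: 0.67 SD

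An effect of 0.7 SD is therefore a reasonable point at which to compare methods.

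**2. What adjustment can remove.** Take equal variance σ² at both visits and correlation ρ. The variance of change is 2σ²(1 - ρ). After regression on baseline it is σ²(1 - ρ²). The ratio is (1 + ρ)/2, so baseline alone explains (1 - ρ)/2 of the variance of change: 2.5% at ρ = 0.95, 5% at 0.9, 10% at 0.8, 15% at 0.7.

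**3. Closed-form gain.** If the unadjusted test has 80% power, adjusted power is Φ(2.802/√ratio - 1.960).
- ρ = 0.9: 2.802/√0.95 = 2.874, power 82.0%
- ρ = 0.7: 2.802/√0.85 = 3.039, power 86.0%

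This ignores the two degrees of freedom spent. With an approximate allowance for that cost, power is about 78 to 79% if nothing is explained and 80 to 81% at 5%.

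**4. Simulation.** n = 60, effect 0.7 SD, normal errors, complete data, 20,000 replicates (Monte Carlo SE about 0.3 points). Assumed: blocks of 4 within baseline above/below the mean by sex, and all explained variance due to baseline. The planned route is Shapiro-Wilk at 0.05 in each arm, then t-test or Mann-Whitney. The adjusted route is least squares on arm, baseline and sex, with rank ANCOVA if residuals fail Shapiro-Wilk.

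| Explained | Planned | Adjusted | Difference | CI width, model / t-test |
|---|---|---|---|---|
| 0% | 76.0 | 75.7 | -0.3 | 1.005 |
| 5% | 75.8 | 77.1 | +1.3 | 0.979 |
| 10% | 76.5 | 80.0 | +3.5 | 0.952 |
| 15% | 76.9 | 82.1 | +5.2 | 0.925 |

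A separate run of 3,000 replicates gave 76.9 against 76.1 at 0%, 76.4 against 78.8 at 5%, and 77.6 against 82.5 at 15%: differences of -0.8, +2.4 and +4.9. None of the figures shows a gain from sex, which had no effect in the model that generated the data.

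**5. Validity.** With normal data, null rejection for the t-test was 4.9 to 5.2% at 0% explained, 4.2 to 4.6% at 5% and 2.8 to 2.9% at 20% (n = 50 and 70; explained share split equally between baseline and sex). With complete data the bias of the unadjusted difference was at most 0.005 SD. Across all scenarios in the main simulation, null rejection was 2.5 to 5.2% for the planned route and 4.8 to 5.7% for the adjusted route.

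**6. Why a rank counterpart is needed.** At 0% explained, least squares alone loses power against the planned route when errors are not normal:
- t(5): 81.8 to 76.2 (-5.6)
- t(3): 93.2 to 80.4 (-12.8)
- lognormal (sigma 0.8): 98.2 to 78.7 (-19.5)

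With the rank ANCOVA fallback the three become 81.1, 92.7 and 98.2, changes of -0.7, -0.5 and 0.0.

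**The case against.** The strongest case against is that this hardly matters. The test is valid, no power target exists to be missed, and a pilot sized by logistics is limited mainly by its size: at an effect of 0.4 SD with normal errors and 5% explained, power is 33.0% planned and 34.5% adjusted. If the two BMI Z-scores are highly correlated, the gain is at most about 2 points, and it is slightly negative if nothing is explained. BMI Z-score is already computed from sex and age (Outcome measures), so sex may add little. All of this stands. It makes the point minor, but does not remove it, because the change is nearly free.

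Three stronger readings are tempting.

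- **That the unadjusted test is wrong because randomisation was stratified.** It is not. Ignoring prognostic strata makes it conservative; it neither biases the difference nor inflates type I error.
- **That precision is certainly being lost.** Nothing in the documents shows that baseline or sex predicts change. Larger gains appear in some non-normal scenarios (lognormal, 0.4 SD, 15% explained: 55.4 against 68.6), but the documents support neither that error shape nor that explained share, and the two routes check normality differently.
- **That the missing-data rule strengthens the case.** Under that rule, for absent children, "they will be replaced by their baseline measurement", so their change is zero. With 20% replaced and nothing explained, the planned route had 61.9% power under a per-arm normality check, against 64.5% for the model with fallback. Under a pooled check the planned route had 64.6%. The apparent gain comes from the choice of check, so no replacement figures are used here. Whether the replacement rule is sound is a separate question.

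The reading that non-normal data lead to the Mann-Whitney test is also an inference. The text places the two tests beside the Shapiro-Wilk check, but ties the distribution explicitly only to how data are presented.

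**Conclusion.** The point holds as a minor matter of precision. The planned comparison is valid but may be less precise than the stratified design allows. At n = 60, 0.7 SD, normal errors and complete data, adjustment is worth about -1 to 0 points of power at 0% explained, +1 to +2 at 5% (ρ = 0.9 if baseline alone) and about +5 at 15% (ρ = 0.7).

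The direction follows from the design. The size rests wholly on assumed effect, correlation, error distribution, strata and block size. Sex belongs in the model because it is a stratifier, not because a gain from it has been shown.

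**What to change.** If outcome data by arm have not been examined, document that and prespecify:

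1. **Primary:** a linear model of 4-month BMI Z-score (or its change) on arm, continuous baseline BMI Z-score and sex, reporting the adjusted mean difference and 95% CI.
2. **Rank counterpart:** rank ANCOVA (ranked change on arm, ranked baseline and sex) or a rank test stratified by the randomisation strata, with a stated normality criterion on model residuals. Say that its p-value does not test the mean difference defined under Outcomes and may disagree with the reported interval.
3. **Sensitivity:** the planned unadjusted t-test and Mann-Whitney test.

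If outcome data by arm have been seen, keep the planned test as primary and report the model as a labelled post hoc analysis. The file is dated 10/06/2021 and the programme runs from March to July 2021, so this version postdates the start and, if the date means October, the end.

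**Cost.** No new data are needed. The price is two degrees of freedom (0.4 to 0.6 points of power against the t-test under normal errors when nothing is explained, n = 50 to 70), null rejection of up to about 5.7% for the model with fallback, a choice of method that still depends on the data, and a documented change to an already published protocol.

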Study measurements will be performed at baseline and at 4 months. The primary outcome (BMI Z-score), waist circumference and triceps skinfold, will be measured by a person blinded to the allocation group and trained in the measurement of these variables. These anthropometric measurements will be carried out at the participants' homes in an outdoor area. Hygiene measures and recommendations will be followed to reduce the risks of contagion (use of NK95 face masks, plastic face shield, surgical suit, gloves, etc. short exposure time and disinfection of materials). Measurements will be made in less than 15 minutes. Before the home visit, a questionnaire will be sent to screen for possible symptoms related to COVID-19. Lifestyle questionnaires will be conducted online.

Primary outcome

- **BMI Z-score:** The measurement will be obtained using the sex, age, weight (kg) and height (m) of the participants. The height and weight will be combined (kg/m²) to obtain the BMI Z-score, expressed in units of standard deviation. Using The WHO Anthro Plus software.²⁵

Secondary outcomes

- **Weight:** To obtain the weight (kg), a TANITA SC-240 will be used. The measurement will be used to obtain the BMI Z-score.²⁶

- **Height:** The SECA 213 stadiometer will be used, following the Frankfurt plan. This measure will be used to obtain the BMI Z-score.²⁶
- **Waist circumference:** A Lufkin metallic anthropometric tape will be used. The umbilical scar will be taken as reference.²⁶
- **Body fat:** It will be estimated with the measurement of the tricipital skinfold, using a formula validated for Mexican children. To take the tricipital skinfold, the ISAK methodology will be followed.^{27,28}
- **Relative fat mass:** This is an estimator of total body fat. A formula carried out with children (8-14 years) will be used where the data of waist circumference (cm), height and sex (0 boys and 1 girls) will be needed.²⁹
- **Nutrition knowledge:** A questionnaire designed by the study team will be used to assess knowledge on nutrition. It consists of 32 questions on nutrition and health.

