- **Food consumption:** Some questions from the semi-quantitative food frequency questionnaire from the National Health and Nutrition Survey were used.³⁰ We asked about the frequency of consumption of ultra-processed foods (sweet beverages, fried foods, cakes and cookies) and healthy foods (fruits, vegetables and water) in the previous 7 days. For each food, the size of the portion consumed was asked, considering an average portion established in the FFQ.
- **Physical activity and sedentary activities:** The physical activity and sedentary lifestyle part of the questionnaire “The Health Behavior in School-aged Children” (HBSC) was used, which is a validated lifestyle questionnaire for school-age children.³¹ It consists of 9 questions, 5 questions related to the time and frequency of physical activity and 4 to sedentary activities.
- **Nutrition knowledge:** a questionnaire designed by the research team (not validated) was used to assess the knowledge on nutrition and health. It consists of 32 questions with multiple choice answers. The results were evaluated on a scale from 0 to 10, the more correct answers, the greater score.

- **Quality of life:** The PedsQL™ (Pediatric Quality of Life Inventory) questionnaire was used, which was designed to assess quality of life aspects in both healthy pediatric patients (2 to 18 years old) and those with chronic diseases. The questionnaire consists of 23 questions about physical, emotional, social and school functioning. The responses are on a 5-point likert scale (never = 0 to always = 4). The score for each item is reversed and transformed to a linear scale of 0–100, with a higher score indicating a better quality of life.³²
- **Retention:** It will be evaluated with the percentage of participants (intervention and control group) who complete the intervention and the measurements at 4 months.
- **Participation or attendance of schoolchildren:** It will be evaluated with the percentage of attended intervention sessions and with the percentage of participants who attended all sessions.
- **Parent's participation:** At the end of the study, parents will be asked through an online questionnaire, the number of materials consulted from the program and will be reported as a percentage.
- **Acceptance.** Acceptability will be obtained with a questionnaire applied to children and parents to qualify the intervention, materials and benefits obtained with the intervention.

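### Continuous secondary outcomes are tested as raw changes with no baseline covariate: valid on average, but less precise than baseline adjustment, chiefly for the questionnaire scores

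*Combined protocol and SAP*

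**What the plan says.** The Statistical Analysis section gives one rule for all continuous outcomes. A t-test for independent samples, or else a Mann-Whitney "test will be used to analyze the difference in BMI Z-score and changes in secondary outcomes between groups". Before that, a Shapiro-Wilk test is to describe the distribution, and a two-tailed p-value of at most 0.05 "will be used as the criterion for statistical significance". The section names no regression model, covariance analysis or baseline covariate, and nor does any other section.

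Change is spelled out only for the primary outcome, under Outcomes: "The change in BMI Z-score for each individual will be obtained by subtracting the BMI Z-score value at 4 months minus the baseline value". The natural reading is that changes in the secondary outcomes are formed in the same way.

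The outcomes concerned are nutrition knowledge, physical activity and sedentary behaviour, quality of life, waist circumference, body fat and relative fat mass. Food consumption and acceptance are compared as proportions and are not part of this point. Under Outcome measures, "Study measurements will be performed at baseline and at 4 months". Under Randomization, allocation is "stratified by BMI Z-score and sex, with an allocation ratio of 1:1", so no questionnaire score is balanced by design. Under Sample size, "we decided that it would be a pilot study of at least 50 participants and no more than 70". The Statistical Analysis section also labels changes in the secondary variables as exploratory, and replaces a missing 4-month value by the baseline value.

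**The concern.** Subtracting the whole baseline value fixes its coefficient at 1. The most precise coefficient is the regression slope of the 4-month value on baseline, which is r when the SDs are equal. If r is well below 1, the subtraction over-corrects and adds baseline noise to the comparison. That is most likely for questionnaire scores. The protocol says of the knowledge test that "a questionnaire designed by the research team (not validated) was used", and the activity and sedentary section has only nine questions.

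Two things are at stake. The first is precision in a trial capped at 70 children for logistical reasons, where the analysis is the one source of extra precision that needs no extra children. The second is how a result reads when the arms happen to differ at baseline on a score that was not stratified: regression to the mean then moves the difference in change even if the programme does nothing.

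**Working it through.** **Inputs from the documents.** 50 to 70 children allocated 1:1, so n = 25 to 35 per arm; one baseline and one 4-month measurement; two-sided 5% level; unadjusted test on change. The sample size was set by logistics with no effect size, SD or power, so there is no figure of the plan's own to reproduce.

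**Assumptions.** Normal outcomes with SD 1 at both visits, correlation r (shown as a range), complete data, and a true effect of 0.5 SD for power. The formulas refer to the t-test, not to Mann-Whitney.

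**Step 1: precision.** The variance per child is 2(1 − r) for change, 1 for the 4-month value alone, and 1 − r² after baseline adjustment. Adjusted over change is (1 − r²) / [2(1 − r)] = (1 + r)/2, so the share of information discarded by change is (1 − r)/2.

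| r | Change 2(1 − r) | Adjusted 1 − r² | Change / adjusted | Discarded |
|---|---|---|---|---|
| 0.3 | 1.40 | 0.91 | 1.54 | 35% |
| 0.5 | 1.00 | 0.75 | 1.33 | 25% |
| 0.7 | 0.60 | 0.51 | 1.18 | 15% |
| 0.9 | 0.20 | 0.19 | 1.05 | 5% |

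At r = 0.3 to 0.5, 50 children analysed by change are worth 50 × 0.65 = 32.5 to 50 × 0.75 = 37.5 analysed with adjustment; 70 are worth 45.5 to 52.5. Below r = 0.5, 2(1 − r) exceeds 1, so change is then less precise than ignoring baseline.

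**Step 2: power for 0.5 SD** (200,000 simulated trials per setting, change t-test against regression on arm and baseline).

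| r | 25 per arm: change / adjusted | 35 per arm: change / adjusted |
|---|---|---|
| 0.3 | 31% / 44% | 42% / 58% |
| 0.5 | 41% / 51% | 54% / 66% |
| 0.7 | 61% / 67% | 76% / 82% |
| 0.9 | 97% / 98% | 99.6% / 99.7% |

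The 4-month value alone gives 41% (25 per arm) and 54% (35 per arm) at every r, so it beats change at r = 0.3.

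**Step 3: error rate over all randomisations.** With no true effect, the same simulations reject in 4.9% to 5.0% of trials for change and 5.0% to 5.1% for the adjusted test. On average neither is inflated.

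**Step 4: error rate given a baseline gap.** The SE of a chance baseline difference is √(2/n) = 0.283 SD (n = 25) or 0.239 SD (n = 35). The probability of a gap above 0.3 SD is 2[1 − Φ(0.3/0.283)] = 29% or 2[1 − Φ(0.3/0.239)] = 21% for each outcome. A gap D moves the expected difference in change by −(1 − r)D. For D = 0.3 that is 0.15 SD at r = 0.5 and 0.21 SD at r = 0.3. With 25 per arm the SE of the change contrast is √(2 × 1.0/25) = 0.28 and √(2 × 1.4/25) = 0.335, so the shift is about 0.5 to 0.6 of an SE. Among simulated trials with a gap above 0.3 SD and no true effect, the change test rejects in 9% (r = 0.5) to 11% (r = 0.3) with 25 per arm, and in 11% to 13% with 35 per arm. The adjusted test stays at 5%.

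**Step 5: effect of the planned imputation.** If a fraction m of 4-month values is replaced by baseline, the analysed correlation becomes (1 − m)r + m = r + m(1 − r). With m = 20% (assumed), r = 0.3 becomes 0.44 and the variance ratio falls from 1.54 to 2/1.44 = 1.39; r = 0.5 becomes 0.60 and the ratio falls from 1.33 to 2/1.60 = 1.25.

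**The case against.** The strongest reply is that nothing here is invalid. The change comparison is unbiased under randomisation and holds its level, the plan calls these outcomes exploratory, and no secondary outcome has a power target to miss. All of that stands. It makes this a gain forgone, not an error.

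A reader might infer that the plan turns baseline differences into false effects, or that an arm starting lower will appear to improve. The documents do not support that as a general statement. The distortion exists only given an imbalance actually seen, is a tendency of about half an SE for a 0.3 SD gap, and works in both directions.

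A reader might also infer that all the questionnaires are unstable. Only the knowledge test is described as not validated; the protocol calls the activity questionnaire validated, and quality of life uses a published instrument. Validation does not settle how strongly scores correlate over 4 months, so a range for r is the honest position, and at r = 0.7 the gain is modest. For waist and body fat, r near 0.9 is plausible and the gain is then close to nil.

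Baseline imputation shrinks the gain but does not remove it. It is a separate problem that adjustment does not solve. Finally, the same sentence of the plan governs the primary outcome, so one edit should cover both.

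**Conclusion.** The point holds as a matter of precision. Testing raw change without a baseline covariate discards 35% to 15% of the information at r = 0.3 to 0.7, which matters mainly for knowledge, activity and sedentary behaviour, and quality of life. At r = 0.9, assumed for waist and body fat, it discards about 5%. Given a chance gap above 0.3 SD, expected in 21% to 29% of trials for each outcome, the false-positive rate is roughly 9% to 13% at r = 0.5 to 0.3 instead of 5%.

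These figures rest on assumed correlations, equal SDs, normality and complete data. They do not show that the planned secondary analysis is biased or that its overall error rate is inflated. Because the outcomes are exploratory, this is an improvement worth making, not a condition for a valid trial. It is still worth making: the outcomes serve the first secondary objective, are tested at the 5% level, and come from a pilot intended to precede a definitive study.

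**What to change.** In Statistical Analysis, replace the unadjusted test of changes by a rule of this kind:

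> For each continuous outcome measured at both visits, the 4-month value will be regressed on study arm, with the child's own baseline value of that outcome, sex and baseline BMI Z-score as covariates. The adjusted mean difference will be reported with its 95% confidence interval, using heteroscedasticity-robust standard errors for every outcome. Raw changes will be reported descriptively.

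Using robust standard errors throughout removes the data-driven switch between t-test and Mann-Whitney. The same sentence should serve the primary outcome, where baseline BMI Z-score is already the child's own baseline and enters once. The nine activity and sedentary questions have no stated summary score, so the variable to be analysed must be defined before the model can be applied to them.

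The cost is a few sentences and a standard linear model. Completing the baseline anthropometry and lifestyle questionnaires is already an eligibility condition, so no extra children or visits are needed. With 50 children, three covariates reduce the residual degrees of freedom from 48 to 45. The team should confirm that its planned software provides the robust standard errors.
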